5.5.3 Emergency Unblinding Procedures

Breaking of the study blind should only be performed where knowledge of the treatment is absolutely necessary for further management of the participant

There will be no central unblinding facility but the on-site pharmacy will hold the unblinding information held in sealed envelopes. Thus unblinding (emergency or otherwise) can be carried out by a pharmacist 24 hours a day, 7 days a week, if requested by a senior clinician (normally a consultant). The name of the clinician requesting the unblinding and the reason for it will be sent to the Chief Investigator via e-mail. Reasons for unblinding will be collected via the e-CRF. Unless there is a clinical requirement, the blind will not be broken to the trial team until after data entry is complete and the database locked. Details of the unblinding will be kept in pharmacy.

In the event of SUSAR, the Co-Sponsor will be able to unblind by the same mechanism as above.

CR007-T01 v4.0 PIPIN Protocol Version 5.0 17/05/2019 Page **20** of **45**

5.6 WITHDRAWAL OF STUDY PARTICIPANTS

Participants are free to withdraw from the study at any point or a participant can be withdrawn by the Investigator. Pre-specified investigator initiated indications for study withdrawal includes:

- Consent withdrawn
- SUSAR
- Fetal demise in utero
- If the participant develops severe pre-eclampsia or HELLP syndrome
- The clinical team judge that immediate delivery is advised, for example in the case of development of severe sepsis or evidence of fetal compromise.

Note that delivery is not a reason for withdrawal as this is an outcome.

If withdrawal occurs, the primary reason for withdrawal will be documented in the participant's medical records and CRF if possible. The participant will have the option of withdrawal from:

- (i) Taking the study medication, with continued study procedures and collection of clinical and safety data
- (ii) all aspects of the trial but continued use of data collected up to that point

If a participant wishes to withdraw from the trial, the trial team will be informed and withdrawal will be recorded in the medical notes, along with the aspects from which they wish to withdraw.

Participants that withdraw following administration of the first dose of intervention or any doses thereafter will not be replaced. Data will continue to be collected where possible to allow intention to treat analysis.

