2.2.2 Secondary Endpoints

Secondary Endpoints:

- 1) Retention, adherence and ability to collect clinical outcomes from participants
- 2) Time to delivery from presentation and gestation at delivery
- 3) Contraction frequency as monitored at presentation and from randomisation to delivery or cessation of regular uterine activity.
- 4) Maternal markers of inflammation including, but not limited to: IL-6, IL-10, IL-13, IL-17, TNFa, IL-1RA, sTNF-RI, sTNF-R2, and HO-1, as well as levels of the soluble IL-6R and the inhibitor spg130 (abbreviated hereafter to 'Inflammatory Profile')
- 5) Fetal measures of inflammation including but not limited to: (cord IL-1, IL-6, IL-8, sIL-6R and sgp130.
- 6) Adverse events (maternal and fetal)
- 7) Time from time first seen in an acute obstetric care setting to administration of trial medication as documented in the participant medical records.
- 8) Compliance with 7 days of blinded treatment
- 9) Acceptability of the trial to those who have participated
- 10) Pharmacokinetic parameters as compared with current published data
- 11) Maternal outcomes:
 - a. Proven maternal infection
 - b. Safety of intervention to mother (self-reported AEs and biochemical monitoring of liver function tests and creatinine kinase).
 - c. Pre-labour ROM
 - d. Duration, location and level of care of hospital stay following presentation with suspected preterm labour AND following delivery.
- 12) Neonatal outcomes:
 - a. Details of in utero transfers including mode of transport required
 - b. Gestational age at delivery, morbidity and mortality, birthweight, duration and location of hospital stay post-delivery and up to 28 days post EDD.
 - c. Safety of intervention

CR007-T01 v4.0 PIPIN Protocol Version 5.0 17/05/2019 Page **14** of **45**

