Compliance (number of tablets taken) will be collected from the participants' medical records and at the day 7 trial visit (from the participant's diary) and the returned medication bottles. Serum pravastatin levels will also be taken to evaluate compliance.

Timing from presentation to first dose administered

Timing of presentation to first treatment dose administered will be collected from the participants' medical records.

Delivery, post-natal and neonatal outcomes

At the time of delivery, secondary outcomes of gestational age at delivery, markers of fetal and maternal inflammation and pravastatin levels will be collected (via medical records and maternal and cord blood samples).

Maternal and neonatal outcomes will be monitored and information extracted from the participants medical records until EDD + 28 days.

Acceptability of the Trial

This will be collected at two points:

- 1) Percentage uptake of eligible participants to the trial
- 2) At or near 28 days post EDD, participants will be contacted using their preferred method of contact, thanked for their involvement and asked for feedback.

Stopping Rules

We have set the following safety rules for PIPIN based on maternal and neonatal deaths that are possibly or definitely related to IMP. We have based these rules on the expected frequency of maternal and neonatal deaths in the population.

CR007-T01 v4.0 PIPIN Protocol Version 5.0 17/05/2019 Page **16** of **45**

We do not anticipate that there will be any maternal deaths (maternal death rate in the UK is 8.5 per 100,000). So in n=40 women we would not expect any deaths – we would need to recruit almost 12,000 women to expect 1 death.

We anticipate that the death rate of babies in the PIPIN population will be at least 6% (based on the Oracle study, which also recruited women in preterm labour (Kenyon et al. 2001). The Oracle study recruited women suspected clinically to be in preterm labour; in PIPIN we will recruit women in whom a "test" has additionally confirmed the onset of preterm labour, hence preterm birth (with associated neonatal death) is more likely to occur in PIPIN).

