Participants will be contacted by their preferred method of contact and acceptability of the trial discussed with them.

CR007-T01 v4.0 PIPIN Protocol Version 5.0 17/05/2019 Page **25** of **45**

The table below summarises this information.

Assessment or outcome	Screening	Randomisation	Day 1	Daily until discharge	Day 7	At Delivery	28 days post EDD
Clinical Measures				J			
Blood pressure	Х						
Fetal Fibronectin / Cervical Length	Х						
/ cervical dilation (one only required)	x						
Contraction Frequency	Х		Х	Х	Х		
Biochemical Measures							
Urea		Х	Х				
Serum creatinine		Х	Х				
Albumin		Х	Х		Х		
Liver transaminases		Х	Х		Х		Х
Inflammatory Profile		Х	Х	Х	Х	Х	
Haematological Measures							
Haemoglobin		Х					
Maternal							
Maternal mortality/ morbidity		Х	Х	Х	Х	Х	Х
Serious adverse events or reactions		Х	х	x	х	x	x
Routine CTG		Х	Х	Х	Х		
Serum Pravastatin			Х	Х	Х	Х	
Fetal & Neonatal Measures							
Gestational age (from EDD by ≤ 16 week scan)	х					x	
Cord inflammatory profile						Х	
Cord pravastatin levels						Х	
Apgar score at 1,5,10 minutes						Х	
Congenital anomalies	Х					Х	
Neonatal mortality/ morbidity						Х	Х
Length of maternal and perinatal hospital stay and location						х	X

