10.2 PROPOSED ANALYSES

Measures to be reported:

Primary outcome data

1. Trial uptake: eligible participants as compared with recruitment.

Secondary Outcome Data

- 1. Routine participant demographics including past medical history and drug history
- Any additional treatments received during inpatient stay (including magnesium sulphate, antibiotics, syntocinon / other methods of induction/augmentation and steroids)
- 3. Retention, adherence and ability to collect clinical outcomes from participants
- 4. Time from presentation with threatened preterm labour to delivery of first dose of IMP.
- 5. Time from presentation to acute care and assessment services with suspected preterm delivery to delivery itself, as well as gestation at delivery
- 6. Contraction frequency during treatment course, from presentation to delivery or cessation of regular uterine activity.
- 7. Bloods: Liver function tests, creatinine kinase levels (side effects), maternal and cord inflammatory profile (see 2.2.2 for details of measures within the inflammatory profile).
- 8. Compliance with treatment
- 9. Adverse events
- 10. Acceptability of the trial following completion of the protocol
- 11. Other clinical outcomes
 - a. Maternal outcomes:
 - i. Proven maternal infection (See Appendix 4: Glossary of Terms for definition)

CR007-T01 v4.0 PIPIN Protocol Version 5.0 17/05/2019 Page **29** of **45**

- ii. Safety of intervention to mother (self-reported AEs and biochemical monitoring of liver function tests and creatinine kinase).
- iii. Pre-labour ROM
- iv. Duration, location and level of care of hospital stay following presentation with suspected preterm labour AND following delivery.
- b. Neonatal morbidity and mortality, safety of intervention, gestational age at delivery, birthweight, duration, location and level of care required following delivery. If in utero transfer occur, cause of method of transport used.
- 12. Pharmacokinetics of pravastatin

Participant uptake the study will involve a direct analysis of eligible participants presenting to acute care and assessment services compared with recruitment. Secondary outcomes 1 and 2 will be used to perform subgroup analysis and identify potential confounders between treatment and placebo arms. Outcomes 3 - 11 will be used to directly compare treatment and placebo arms of the trial, and inform design for a large scale trial in the future.

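### Death of the baby is an outcome only after live birth, so in a trial meant to prolong pregnancy the mortality comparison can favour the arm that delivers later

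*Protocol*

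**What the plan says.** Wherever the protocol makes death of the baby an outcome, it is a neonatal one:

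- Section 2.2.2, item 12b, under the neonatal outcomes: "Gestational age at delivery, morbidity and mortality, birthweight, duration and location of hospital stay post-delivery and up to 28 days post EDD".
- Section 7.2, schedule of assessments, a row for "Neonatal mortality/ morbidity", collected at delivery and 28 days after the EDD.
- Section 10.2, item 11b: "Neonatal morbidity and mortality, safety of intervention, gestational age at delivery, birthweight".

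Section 10.2 then states that "Outcomes 3 - 11 will be used to directly compare treatment and placebo arms of the trial". No endpoint, schedule row or listed analysis names stillbirth, fetal death or perinatal death.

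Section 5.6 lists "Fetal demise in utero" among the investigator-initiated indications for withdrawal. The same list contains "The clinical team judge that immediate delivery is advised, for example in the case of development of severe sepsis or evidence of fetal compromise". It is followed by the remark "Note that delivery is not a reason for withdrawal as this is an outcome".

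Section 3 describes "safety rules for PIPIN based on maternal and neonatal deaths". It goes on to give an expected death rate for babies of at least 6%, and its triggers refer simply to deaths.

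**The concern.** Section 2.1.2 asks whether pravastatin prolongs the time to delivery. If it does, treated pregnancies spend longer at risk before birth, in a condition that section 1.1 links to infection and inflammation. A baby that would have died after birth may then die in utero. The total number of deaths is the same, but the death no longer counts as neonatal. A treatment that changes when birth happens also changes which deaths are eligible for a neonatal count, so that count is not a neutral comparison of the arms.

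At stake is how a secondary outcome is read and, because section 10.2 uses these outcomes to inform a larger trial, whether the same definition is carried into that trial.

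**Working it through.** **Inputs from the protocol.** Expected death rate of babies 6%, with a doubling as the level of concern (section 3); about 20 women per arm (40 women, 1:1, sections 4.1 and 5.5.1); triggers of 1 death in the first 10 and 2 in the first 20 on pravastatin (section 3).

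**Assumptions.** The share f of deaths that occur in utero in one arm is varied from 25% to 75%, because the documents give no fetal death rate. The 6% is treated as a total of fetal plus neonatal deaths. The documents do not say whether it includes stillbirths.

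**Step 1: the plan's own figures.** Doubled rate 2 × 6% = 12%. Expected deaths 0.12 × 10 = 1.2 and 0.12 × 20 = 2.4, which round down to the stated triggers of 1 and 2.

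**Step 2: effect on the mortality comparison.** Hold the total at 6% in both arms. In the comparison arm all deaths are neonatal; in the other arm a share f is fetal.

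Neonatal rate per randomised pregnancy = 0.06 × (1 − f). Neonatal rate per live birth = 0.06 × (1 − f) / (1 − 0.06 × f). Each risk ratio is against 6%.

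| f | Per randomised pregnancy | Risk ratio | Per live birth | Risk ratio |
|---|---|---|---|---|
| 25% | 4.5% | 0.75 | 4.6% | 0.76 |
| 50% | 3.0% | 0.50 | 3.1% | 0.52 |
| 75% | 1.5% | 0.25 | 1.6% | 0.26 |

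The true risk ratio for death is 1 in every row. Changing the denominator to live births does not repair it.

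**Step 3: effect on the safety rule, if it is read as neonatal deaths only.** Every death is treated as countable, although the rule also requires a suspected relation to the study drug. Take the total at the level of concern, 12%, with f = 50%. The neonatal rate is 0.12 × 0.5 = 6%, which equals the expected background rate.

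- P(at least 1 of 10): 1 − 0.88^10 = 0.721 at 12%; 1 − 0.94^10 = 0.461 at 6%.
- P(at least 2 of 20): 1 − 0.88^20 − 20 × 0.12 × 0.88^19 = 0.711 at 12%; 1 − 0.94^20 − 20 × 0.06 × 0.94^19 = 0.340 at 6%.

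For f = 25% the two probabilities are 0.611 and 0.548; for f = 75% they are 0.263 and 0.120.

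**Step 4: counting both kinds of death.** With fetal plus neonatal deaths per randomised pregnancy, 6% stays 6% and 12% stays 12% for any f. The risk ratio in step 2 returns to 1, and the probabilities in step 3 stay at 0.721 and 0.711.

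**The case against.** **Fetal deaths have another route into the comparison.** Fetal adverse events are secondary endpoint 6, adverse events are item 9 of section 10.2 and so fall within the outcomes compared between arms, and section 11 records them from consent to EDD + 28 days. The list in section 11.5 of events not treated as serious does not exclude fetal death. This stands: a fetal death need not be invisible, and with about 20 women per arm a careful reader could add the two tables. It is still not a defined outcome. The death criterion for a serious event in section 11.1 refers to the trial participant without naming the fetus, and section 11.3.2 leaves expected progression of the underlying condition out of the adverse event log.

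**A reader might infer that withdrawal itself loses these deaths or flatters retention.** The documents do not support that. Option (i) in section 5.6 keeps clinical and safety data coming, and that section continues collection where possible for the intention-to-treat analysis. Option (ii) is the woman's choice and keeps data up to that point, so a fetal death that prompted it is already recorded. Women who withdraw after a first dose are not replaced. Section 6.4 also reads the list as reasons for withdrawing study medication. The problem lies in the endpoint definition.

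**A reader might infer that the safety rule plainly excludes fetal deaths.** It does not. One sentence says neonatal deaths, the next paragraphs speak of babies and of deaths. That is an ambiguity to resolve.

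**The size is assumed, and the trial is small.** Both are true. Treatment lasts at most 7 days, and mortality is part of one secondary item in a feasibility study.

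**Conclusion.** The point holds as a weakness in the definition of a secondary outcome. Mortality of the baby is counted only after live birth, the hypothesised drug effect is longer pregnancy, and the arms are compared directly. The direction of the possible distortion is therefore known: it favours the arm with longer pregnancies.

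Its size cannot be estimated from the documents. Across assumed shares of 25% to 75% of a constant 6% total, the apparent risk ratio runs from 0.75 to 0.25 with no true benefit. These figures assume that the shift occurs in one arm only and that the total is unchanged. The loss of sensitivity in step 3 applies only if the safety rule is read narrowly.

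The consequence is for interpretation of a secondary outcome and for the design of the later trial. The primary recruitment endpoint is untouched.

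**What to change.** 1. In sections 2.2.2 and 10.2, define the mortality outcome as death of the fetus or infant from randomisation to EDD + 28 days, with all randomised pregnancies as the denominator and the fetal and neonatal components shown separately. Add fetal death to the schedule in section 7.2.
2. In section 3, reconcile the three descriptions of the deaths covered by the safety rule and state whether fetal deaths are included.
3. Reconcile section 5.6 with section 6.4 and with its own remark that delivery is an outcome, so that fetal demise and clinically indicated delivery are recorded as outcomes with follow-up retained. Any consequence for study drug is a separate clinical matter for the sponsor.

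The cost is a protocol amendment, with the approvals that section 14.1 requires, and a small addition to the case report form. No new visit is needed, because maternal and neonatal records are already reviewed to EDD + 28 days.

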11.4 ASSESSMENT OF AEs AND SAEs

Each AE must be assessed for seriousness, causality, severity and ARs must be assessed for expectedness by the Principal Investigator or another suitably qualified physician in the research team who has been delegated this role.

For randomised double blind studies, AEs will be assessed as though the participant is taking active IMP. SUSARs will be unblinded by ACCORD before they are reported to REC and CA (by ACCORD).

The Chief Investigator (CI) may not downgrade an event that has been assessed by an Investigator as an SAE or SUSAR, but can upgrade an AE to an SAE, SAR or SUSAR if appropriate.

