14.7 CONTINUATION OF DRUG FOLLOWING THE END OF STUDY

When the participant delivers her infant or completes 7 days of treatment (whichever occurs soonest), the drug will stop being administered.

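### Section 5.6 makes events such as a decision for immediate delivery grounds for leaving the study, against its own note and Section 6.4, so later outcomes can be lost where prognosis is worst

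*Protocol*

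**What the plan says.** Protocol Section 5.6 introduces its list with "Pre-specified investigator initiated indications for study withdrawal includes". Apart from withdrawn consent, the list holds four clinical events: a SUSAR, fetal demise in utero, "If the participant develops severe pre-eclampsia or HELLP syndrome", and "The clinical team judge that immediate delivery is advised, for example in the case of development of severe sepsis or evidence of fetal compromise". The line after the list reads "Note that delivery is not a reason for withdrawal as this is an outcome".

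When withdrawal occurs, the participant can choose between two levels:
- (i) stopping the trial drug only, while study procedures go on and clinical and safety information is still gathered
- (ii) a full exit, put as "all aspects of the trial but continued use of data collected up to that point"

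The section ends by saying that women who withdraw after a first dose are not replaced, and that their data will still be gathered, so far as possible, for intention to treat.

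Three other sections bear on this:
- **Section 6.4** refers back to the same reasons, but as withdrawal of study medication.
- **Section 14.7** ends dosing in any case: "When the participant delivers her infant or completes 7 days of treatment (whichever occurs soonest), the drug will stop being administered".
- **Section 10.2** promises analysis by intention to treat.

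**The concern.** A decision for immediate delivery comes just before the delivery endpoint. If it counts as leaving the study, the woman exits shortly before her time to delivery, gestation at delivery, cord-blood profile and neonatal outcome would be recorded. All of these are secondary endpoints in Section 2.2.2. Severe pre-eclampsia, HELLP, fetal demise and a SUSAR also carry information about prognosis, and liver function is a safety endpoint there.

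Any loss that follows from this list is therefore tied to outcome. With about 20 women per arm, a few such losses could shift the estimates that Section 10.1 says will help decide whether a large trial is warranted. They would also blur retention, itself a secondary endpoint, by mixing investigator-triggered exits with women who chose to leave.

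**Working it through.** The protocol states no figure on this point and Section 10.1 gives no power calculation, so there is nothing to reproduce. The check is a comparison of the text, followed by an illustration of size.

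**1. Which level of withdrawal is meant?**

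| Place | What it implies for the listed events |
|---|---|
| 5.6, introduction to the list | The woman is withdrawn from the study |
| 5.6, note after the list | Delivery must not cause withdrawal, because it is an outcome |
| 5.6, options (i) and (ii) | Either level, as the woman chooses |
| 6.4 | Only the medication is withdrawn |

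These cannot all be followed. A site whose team advises immediate delivery cannot tell from the text whether the woman stays in the study.

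**2. Does a medication-only reading settle it?** Not for the whole list. Dosing stops at delivery or day 7 (Section 14.7), so for an immediate delivery a drug stop adds little. The list is not confined to the 7 treatment days, while follow-up runs to EDD + 28 days (Section 3). After day 7 there is no trial drug left to stop, so a listed event could then only mean leaving the study.

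**3. What survives if option (ii) is taken?** The triggering event should. Section 11 requires adverse events to be recorded to EDD + 28 days, and Section 11.7 asks for follow-up to a final outcome. Those duties do not secure the later delivery, cord-blood, day-7 liver and neonatal outcomes. Option (ii), read literally, keeps only what was collected before exit, which also sits badly with the adverse-event duty.

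**4. Is the loss one-sided for SUSARs?** Section 11.4 has adverse events assessed as though the woman were on active drug, so a suspected SUSAR can arise in either arm. The sponsor's office unblinds before regulatory reporting. Loss would fall on one arm only if withdrawal waited for that unblinding, and the protocol gives no timing.

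**5. Illustration of size.** About 20 per arm comes from Section 3 (Stopping Rules) and the 1:1 allocation. Everything else is assumed: m emergency deliveries at day 3, the remaining women averaging 30 days, and loss in one arm only.

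Mean with all women kept = ((20 − m) × 30 + m × 3) / 20. Mean with the m women lost = 30.

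| m | Mean, all kept | Mean, m lost | Upward shift (days) |
|---|---|---|---|
| 1 | (570 + 3)/20 = 28.65 | 30 | 1.35 |
| 2 | (540 + 6)/20 = 27.30 | 30 | 2.70 |
| 3 | (510 + 9)/20 = 25.95 | 30 | 4.05 |

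The same mechanism acts on a proportion. With an assumed 6/20 = 30% true event rate in each arm, losing 1, 2 or 3 women with the event from one arm gives 5/19 = 26.3%, 4/18 = 22.2% or 3/17 = 17.6%, against 30% in the other.

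If option (i) and continued collection apply to every woman, nothing is lost and the shift is zero.

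**The case against.** The strongest reply is that continued collection is the stated default. Option (i) comes first, both options belong to the participant, and nothing says the investigator imposes option (ii). A woman may leave at any time in any case. Section 6.4 reads the reasons as stopping medication, and Sections 3 and 7.2 take maternal and neonatal outcomes from records to EDD + 28 days without a visit. This largely stands: data loss is not the planned handling. What it leaves open is that an investigator-triggered event puts full exit before a woman who has not asked to leave, and that the promise of continued collection is qualified.

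Three stronger readings are tempting, and the documents do not support them.
- **SUSAR cases are lost from one arm.** Events are judged as though on active drug, and no text ties withdrawal to unblinding.
- **HELLP cases vanish from the liver-safety data.** The event itself is recorded and followed. At most a later scheduled sample is missed, and only under option (ii).
- **Intention to treat is abandoned.** Missing outcomes weaken that analysis but do not cancel it. Section 10.2 also plans sensitivity analyses and leaves their detail to a statistical analysis plan that is not at hand.

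It is also fair to say that the days figures are invented inputs applied to one arm. The judgement that immediate delivery is needed is made under double blinding. With equal loss in both arms and no drug effect, the difference between arms would be zero, though each arm's own mean would still be too high. Finally, the primary endpoint in Section 2.2.1, the proportion consenting, cannot be affected. The Trial Summary, however, words the primary endpoint to include retention and outcome collection, and those can be.

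**Conclusion.** The concern holds as a defect of wording. Section 5.6 contradicts its own note and Section 6.4 on whether the listed events end study participation or only treatment. Because full exit is on offer even when the investigator triggers withdrawal, later delivery, cord-blood, day-7 liver and neonatal outcomes can be lost in the women with the worst prognosis.

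The size is unknown. It depends on how many women have a listed event, how many of them choose option (ii), and whether the losses differ between arms. The illustrated shifts of 1.35 to 4.05 days are a one-arm worst case on assumed values; the lower bound is zero. This should be corrected because the remedy is cheap, but it does not undermine the feasibility aim.

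**What to change.** Reconcile Section 5.6 with its note and with Section 6.4 by treating two things separately: stopping study medication, and leaving the study. Leave unchanged which clinical events affect treatment; no view is offered on that. Then state that:
- after any investigator-initiated stop, delivery, neonatal and safety data are still collected from records to EDD + 28 days;
- cord-blood and day-7 samples continue under option (i);
- option (ii) applies only when the woman herself withdraws consent to further data collection.

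Recording treatment stop and study exit as separate items would keep the retention endpoint clean.

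The cost is a wording amendment through the route in Section 14.1. No visits are added, because the EDD + 28 day outcomes already come from electronic records.
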